## **Outcome Measure(s)**

### **Primary Outcome Measure**

Name: Oxytocin concentration in plasma

Type: Primary

Time Frame: For 120 minutes after the end of the beginning of intravenous oxytocin infusion

Time Frame: For 60 minutes after the administration of the 102 µg intranasal oxytocin

Description: Blood will be sampled at specified intervals during and after the IV infusion and after the intranasal self-administration. Plasma will be separated, rapidly frozen, and later analyzed for oxytocin concentration. The oxytocin concentrations will be modeled to describe the pharmacokinetics of oxytocin and the bioavailability of oxytocin after i.n. administration. We will also determine the effect, if any, of the covariates sex, age, weight, race, and ethnicity.

## **Analytical Plan**

The parameters of the PK model will be fit to the observed plasma concentrations using NONMEM. Inter-subject variability (e.g., biological variability) will evaluate additive, proportional, and exponential models. Residual intrasubject variability (e.g., noise) will typically require an additive and multiplicative error model. The influence of covariates (e.g., age, sex, weight) on model parameters will be analyzed by serial inclusion / exclusion, with significance determined by the likelihood ratio test ( $p < 0.01$  if the decrease in  $-2 \log$  likelihood exceeds 6.6 ( $\chi^2_{0.99/2}$ ,  $df = 1$ )). Parameters will be estimated using first-order conditional estimate with  $\eta$ - $\epsilon$  interaction. Covariate effects deemed significant by likelihood ratio test will be validated using jackknife crossvalidation [3]. Jackknife cross-validation provides an estimate of the utility of the covariate to inform the pharmacokinetics in a future individual, rather than merely characterize the pharmacokinetics in the individuals from which the model was derived. The jackknife cross-validation divides the data into  $N$  subsets. Each subset leaves out a single individual. The parameters of the model are re-estimated for each subset with and without the covariate being validated. The inaccuracy (mean  $(|measured - predicted|) / predicted$ ), of the model with and without the covariate is measured in the excluded individual. The covariate is only included in the final model if the improvement in model accuracy in the  $N$  iterations is significantly greater than 0. Jackknife crossvalidation helps compensate for NONMEM's ability to identify very small covariate effects that do not

meaningfully contribute to accuracy in future patients. We will study 24 subjects. Bootstrap analysis indicates that the confidence interval for studies of 20 individuals using the LC/MS assay will determine the PK parameters with a corrected confidence range < 20%. A corrected confidence range less 20% implies that mixed effect analysis will distinguish covariate effects in the range of 40% in a study with 20 or more subjects. This is the range at which the covariate effect may be clinically consequential. In practice, mixed-effects analysis with NONMEM is often sensitive to covariate effects smaller than predicted by preliminary analyses. The sample size is increased to 24 to provide stratification by age (3 strata), weight (2 strata), and sex. The crossover design permits accurate determination of i.n. bioavailability and dose linearity despite expected high inter-subject variability in absorption.

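### The jackknife tests covariates that the left-out subjects helped to select, so its accuracy gain favours the covariate and does not estimate utility in a future individual

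*Combined protocol and SAP*

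**What the plan says.** The combined protocol and SAP, under Analytical Plan, sets out a sequence:

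1. Covariates are added and removed serially, "with significance determined by the likelihood ratio test". The criterion is that the fall in −2 log "likelihood exceeds 6.6" on 1 df, given as p < 0.01. No hold-out is described, so all subjects are used.
2. Only the survivors go forward: "Covariate effects deemed significant by likelihood ratio test will be validated using jackknife crossvalidation".
3. The data are split into N subsets: "Each subset leaves out a single individual".
4. Within each subset, "The parameters of the model are re-estimated for each subset with and without the covariate being validated".
5. Relative absolute error in the excluded subject is compared with and without the covariate. "The covariate is only included in the final model if the improvement in model accuracy" over the N iterations is significantly above zero. The test and its level are not given.

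The purpose is stated directly: "Jackknife cross-validation provides an estimate of the utility of the covariate to inform the pharmacokinetics in a future individual". The number of folds follows from "We will study 24 subjects". The candidates named under Outcome Measure(s) are sex, age, weight, race and ethnicity.

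**The concern.** Cross-validation estimates out-of-sample performance only if every data-driven step is repeated without the left-out subject. Here the parameter estimates are out of sample, but the choice of covariate, and of the parameter it acts on, is not. A covariate reaches the jackknife because it fitted these 24 subjects unusually well. Dropping one subject at a time from a data set already known to show the association leaves most of that chance association in place.

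The plan relies on this step as its protection against covariates that do not help in later patients. The covariate model is also one of the study's products: it is part of the primary outcome description, and Study Design mentions adjusting dose to the individual if characteristics alter concentrations. A reader would take the jackknife gain as out-of-sample evidence.

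**Working it through.** **The plan's own figure.** The 0.99 quantile of chi-square on 1 df is 6.635. The tail probability at exactly 6.6 is 0.0102. The stated cut-off reproduces to its printed precision. The plan gives no numerical performance for the jackknife.

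**Why the sign can reverse.** Take a balanced two-level covariate (12/12) with no effect, and an individual log-parameter treated as observed.

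- The LRT statistic is −N·ln(1 − r²). With N = 24, exceeding 6.6 requires r² > 1 − exp(−6.6/24) = 1 − 0.760 = 0.240.
- In-sample root-mean-square error is then multiplied by at most √0.760 = 0.872.
- Leaving one out divides residuals by 1 − 1/24 without the covariate and by 1 − 2/24 with it. The penalty is (23/24)/(22/24) = 1.045.
- The jackknife ratio is therefore at most 0.872 × 1.045 = 0.911. Any such covariate passing the LRT shows at least a 9% apparent reduction in root-mean-square error.
- In new subjects the fitted slope is pure noise. Taking the sample variance as close to the true one, error variance is multiplied by about 1 + 0.240 at the threshold, and √1.240 = 1.114: an 11% loss.

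The leave-one-out penalty is far too small to undo the selection.

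**Simulation on the plan's error measure.** Inputs from the documents are N = 24, cut-off 6.6, leave-one-out folds and |measured − predicted|/predicted. Assumptions not in the documents are between-subject SD of 0.2 to 0.5 on the log scale, K = 1, 5 or 20 independent continuous candidates, and a one-sided 5% paired t-test for retention. All covariates are null. Gains are percentage points of inaccuracy among data sets where the best covariate passed the LRT.

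| SD | K | Passes LRT | Plan's jackknife gain | True gain, new subjects | Selection repeated per fold | LRT hits kept by plan's jackknife |
|---|---|---|---|---|---|---|
| 0.2 | 1 | 1.4% | +2.1 | −2.5 | +0.1 | 12.7% |
| 0.2 | 5 | 7.3% | +2.1 | −2.6 | −0.1 | 14.8% |
| 0.2 | 20 | 26.1% | +2.1 | −2.5 | −0.4 | 13.0% |
| 0.3 | 1 | 1.4% | +3.5 | −4.1 | +0.1 | 12.5% |
| 0.3 | 5 | 6.7% | +3.3 | −4.2 | −0.2 | 10.7% |
| 0.3 | 20 | 25.8% | +3.3 | −4.1 | −0.6 | 11.7% |
| 0.5 | 1 | 1.6% | +6.6 | −8.3 | +1.1 | 14.8% |
| 0.5 | 5 | 7.4% | +6.3 | −8.0 | −0.2 | 11.1% |
| 0.5 | 20 | 27.9% | +6.5 | −8.5 | −1.1 | 11.5% |

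Real effects are also flattered. With slope 0.17 and SD 0.3, the apparent gain is 5.5, 5.7 and 5.3 points for K = 1, 5 and 20. The true gain is 3.7, 2.6 and 1.1, and repeated selection gives 3.8, 3.7 and 2.2.

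**Effect on the final model.** In a wider null search (five covariates on six parameters, SD 0.16 to 0.5), 36% of simulated trials had at least one false LRT hit. The jackknife kept 15.7% of false hits as written and 8.1% with selection repeated. A false covariate reached the final model in 6.6% and 3.5% of trials. Across the runs, retention of false hits was about 9–16% as written and 5–9% nested.

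**The case against.** The strongest objection is that these sizes treat individual parameters as directly observed. The plan's measured values are most naturally plasma concentrations, where assay noise and variability in the other parameters dilute a false gain. This stands. The uncorrected N = 11 ranges in Table 1 imply SD ≈ range × √11/3.92: (1.08 − 0.89)/0.98 × 3.317/3.92 = 0.16 for Cl1, and about 0.24 to 0.25 for V1, Cl2 and V2. A concentration-level run used such SDs, the Table 1 two-compartment model, IV sampling times and 16% residual error, with units of L and L/min assumed. It gave +1.6 points apparent against −2.1 true for Cl1, and +0.8 against −1.0 for V1. For Cl2 and V2 both were near zero, with the jackknife positive in only about half of cases (50% and 44%). That run omitted the intranasal arm. The upper end of the SD range is relevant mainly to absorption and bioavailability, for which the plan expects high variability but gives no value.

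Second, the jackknife is used as a yes/no filter, and the plan says only that it helps compensate for over-sensitive testing. As a filter it works reasonably well, removing roughly 84–91% of false LRT hits. A reader might infer that it is worthless, and the calculations do not support that.

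Third, repeating selection does not recover the true loss. It brings the estimate to about zero where the truth is negative, and it measures the search procedure rather than one covariate. This also stands, and the fix has to say so.

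Fourth, a reader might infer that the jackknife gain will be published as grounds for dose adjustment. The documents do not say this: they tie dose adjustment to characteristics altering concentrations, not to this figure. The Data Sharing Plan releases concentrations with age, weight and sex, so outsiders could rerun a nested check for those covariates, though not for race or ethnicity.

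None of this restores the stated property. A gain computed after full-data selection still does not estimate utility in a future individual.

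**Conclusion.** The point holds as a fault in what the jackknife can be said to estimate. Because selection is not repeated, its gain is biased towards the covariate. At parameter level, null covariates that passed the LRT show about +2 to +7 points when the truth is about −2 to −8.5. On concentrations the bias is smaller, and it may vanish for Cl2 and V2. False hits are kept about 9–16% of the time, against about 5–9% with nested selection. The effect on the final model is modest.

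The direction is firm. The sizes are indicative, since they rest on assumed SDs, numbers of candidates and retention test, and on a linear stand-in for the NONMEM fit. A reader might infer that every reported gain will have the wrong sign. That does not follow: the reversal concerns null covariates, and for the moderate real effect simulated (slope 0.17) the gain was overstated, not reversed. Nor does the point undermine the main objective of absorption rate and bioavailability, which this step does not define. It is worth correcting before the covariate analysis is run.

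**What to change.** Amend the Analytical Plan as follows:

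- Repeat the full inclusion/exclusion search, with the LRT at 6.6, inside each of the N leave-one-out subsets. Predict the left-out subject from whatever that subset selects, and set that subject's gain to zero when it selects no covariate.
- Test a covariate chosen on the full data for retention using these nested predictions, and name the test and its level.
- Report the nested gain as the performance of the selection procedure, together with the share of folds that reselect that covariate. The share is needed because folds may choose different covariates or none.
- Describe any un-nested jackknife figure only as a filter conditional on LRT selection, not as utility in a future individual.

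The cost is computing time for about 24 repeats of a small covariate search and a few sentences of text, with no new data or visits. Retention becomes slightly more conservative; in simulation the loss of power for a 40% effect was under 1 percentage point.

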## Methods and Measures

Equal numbers of adult men and women will be recruited. Sample size will be divided into 3 groups; young (18-39-year-old) middle (40 – 59-year-old) and older (60 – 75-year-old).

Subjects will report to the CTSI Clinical Research Unit (CRU) for two visits, separated by at least 5 days. On study visit one informed consent will be obtained and eligibility verified. Then two intravenous (IV) catheters will be inserted, one in each forearm, with one for drug infusion and the other for blood sampling. After baseline measures, subjects will receive oxytocin (Pitocin®), 14  $\mu$ g (8.2 IU) over 30 minutes. This dose and infusion duration were chosen based on previous studies showing no adverse events in 10 volunteers and our preliminary PK model which predicts that plasma oxytocin concentrations will be above the limit of detection (1 pg/ml) at 120 min. Venous blood samples (5 ml) will be obtained at 2, 5, 10, 20, 30, 40, 50, 65, 90, and 120 minutes after the initiation of oxytocin administration for oxytocin assay.

On study visit 2, one IV catheter will be placed for blood sampling. After baseline measures, subjects will receive 102  $\mu$ g (60 IU) intranasal oxytocin (Tonix-1900, Tonix Pharmaceuticals, Chatham, NJ). Venous blood samples (5 ml) will be obtained at 1, 2, 5, 7, 10, 15, 20, 25, 35, 45, and 60 minutes after the initiation of the oxytocin administration for oxytocin assay. See graph 3 for rationale for the times of sampling.

**Figure 2. A)** PK modeled OXT concentrations in preliminary data compared with published reports. **B)** Fraction of targeted concentration using TCI. 95% prediction intervals from LC/MS or ELISA assays of duplicate samples (n=11).

We will abandon an individual participant's study and schedule another participant should we be unable to successfully place the intravenous catheters.

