### **Sample Size**

We request permission to study up to 30 subjects so that we will have 24 evaluable subjects, respectively, with complete sampling at all time periods. Sample size will be divided into 3 groups; young (18-39-year-old) middle (40 – 59-year-old) and older (60 – 75-year-old).

Sample size was determined using of bootstrap analyses and conventional calculations to estimate the pharmacokinetic parameters within the desired level of accuracy. Table 1 shows the results of 1000 bootstrap replications of the original 11 individuals in the pharmacokinetic study, resampled with N = 11 (the original study size) and N = 20. As expected, the estimates are more precise with increasing study size. The mean and 95% confidence intervals are shown for each parameter.

N	Parameter	Mean	95% Confidence Bound		Range	Correction	Corrected Range
			Lower	Upper			
11	Cl1	0.98	0.89	1.08	20%	2.54	50%
	V1	10.2	8.9	11.9	29%		74%
	Cl2	0.21	0.18	0.24	29%		74%
	V2	7.1	6.1	8.1	28%		70%
20	Cl1	0.97	0.95	1.01	7%	1.88	12%
	V1	10.1	9.6	10.6	10%		18%
	Cl2	0.20	0.20	0.21	8%		16%
	V2	7.0	6.7	7.3	8%		16%

**Table 1** Bootstrap parameter estimates of PK model.

The 95% confidence intervals from the bootstrap are corrected to provide a “best” estimate of the true 95% CI using the upper confidence limit (UCL) method of Browne [1]. As described by Whitehead [10], the 95% UCL correction is  $k/\chi_{(0.95,k)}^2$  where k is N-1, the number of degrees of freedom. As seen in Table 1, the parameters estimated for the initial 11 subjects have a reasonable level of certainty (95% CI < 30% of the mean value) for a small study. However, the corrected CI range from the bootstrap for an N=11 study is closer to 70%. A study with 20 subjects will estimate the parameters within a corrected 95% CI range within 20% of the mean estimated value (Table 1, numbers in red). This is sufficient accuracy to inform the subsequent studies.

Sample size in this study is increased to 24 to permit stratifying by age (3 strata), weight (2 strata), and sex. A corrected confidence range less than 20% (Table 1) implies that mixed effect analysis will distinguish covariate effects in the range of 40% in a study with 20 or more subjects. This is the range at which the covariate effect may be clinically consequential. In practice, mixed-effects analysis with NONMEM is often sensitive to covariate effects smaller than predicted by preliminary analyses.

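### The covariate plan is only a keep/drop rule: it schedules no estimate and interval for dropped covariates and makes no allowance for selection in kept ones, which matters for intranasal bioavailability if it varies widely between subjects

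*Combined protocol and SAP*

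**What the plan says.** The Outcome Measure(s) section, under the primary outcome, sets the aim: "We will also determine the effect, if any, of the covariates sex, age, weight, race, and ethnicity". The Study Design section gives the use: individual dose adjustment, by this group or others, if the characteristics prove to matter.

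The Analytical Plan gives the method. Covariates "will be analyzed by serial inclusion / exclusion, with significance determined by the likelihood ratio test", at p < 0.01 (a drop in -2 log likelihood above 6.6 on 1 df). Then "Covariate effects deemed significant by likelihood ratio test will be validated using jackknife crossvalidation". Finally, "The covariate is only included in the final model if the improvement in model accuracy in the" N iterations is significantly above zero. No significance level, test or sidedness is stated for this last step.

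On size, "We will study 24 subjects", and "Equal numbers of adult men and women will be recruited". The Sample Size section and the Analytical Plan both say that 20 or more subjects can distinguish covariate effects of about 40%, and add: "This is the range at which the covariate effect may be clinically consequential". Table 1, the basis for this, covers Cl1, V1, Cl2 and V2 from 11 subjects given intravenous oxytocin. It has no row for bioavailability (F) or absorption rate. For absorption, the Analytical Plan says only that between-subject variability is expected to be high.

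**The concern.** To determine an effect is to estimate it and say how precisely. The stated procedure answers another question: does the covariate earn a place in a predictive model? Three things follow.

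- A covariate that fails either step is absent from the final model, and no estimate or interval is scheduled for it.
- A covariate that passes is estimated from the data that selected it. Where power is low, only overestimates can pass.
- The plan names 40% as possibly consequential, but no planned analysis compares an estimate or interval with it.

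At stake is what later work on dosing by age, sex or weight can take from this study. Bioavailability is the main objective, and the sample size reasoning does not cover covariate effects on it.

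**Working it through.** **The plan's own figures.** The Table 1 correction is k / chi-square(lower 5%, k): 2.54 for k = 10 and 1.88 for k = 19, as printed. The 40% can be rebuilt from a corrected range of 20% at N = 20:

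- SE of a mean = 20% / 3.92 = 5.1%.
- SE of a 10 v 10 contrast = 2 x 5.1% = 10.2%.
- Full 95% width = 3.92 x 10.2% = 40%.
- Power for a 40% effect at two-sided 0.01 = Phi(40/10.2 - 2.576) = 91%.

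So the statement is coherent for the intravenous parameters at Table 1 precision.

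**Bioavailability: inputs.** Sex contrast of 12 v 12 (24 subjects, equal numbers by sex). True ratio 1.4, from the plan's 40%. The SD of log F is assumed over a range. Error in estimating each subject's F is ignored, which favours the plan. Only the likelihood ratio step is modelled, by a normal approximation.

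**Formulas.**

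- SE = SD x sqrt(2/12).
- Smallest ratio that passes = exp(2.576 SE).
- With a = 2.576 - ln(1.4)/SE, pass rate = 1 - Phi(a).
- Mean log estimate given a pass = ln(1.4) + SE x phi(a) / (1 - Phi(a)).
- 95% interval factor = exp(1.96 SE).

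Example, SD 0.6: SE = 0.245; a = 2.576 - 0.336/0.245 = 1.20; pass rate 11.5%; mean log estimate = 0.336 + 0.245 x 1.69 = 0.750, or 2.12-fold. Simulation gives the same values.

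| Assumed SD of log F | SE | Smallest passing ratio | Pass rate, true 1.4 | Mean estimate if passed | 95% interval: x/÷ | Interval inside 1/1.4 to 1.4 if no true effect |
|---|---|---|---|---|---|---|
| 0.2 | 0.082 | 1.23 | 94% | 1.41 | 1.17 | 97% |
| 0.3 | 0.122 | 1.37 | 57% | 1.52 | 1.27 | 57% |
| 0.6 | 0.245 | 1.88 | 12% | 2.12 | 1.62 | 0% |
| 0.9 | 0.367 | 2.58 | 5% | 3.00 | 2.05 | 0% |

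**Where the interval stops being informative.** Solve 1.96 x SD x sqrt(2/12) = ln 1.4: SD = 0.336 / (1.96 x 0.408) = 0.42. Above this, even an estimate of exactly 1 has an interval that reaches 1.4.

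**Larger true effects.** For a true 2-fold effect, the mean passing estimate is 2.00 / 2.34 / 3.20 at SD 0.3 / 0.6 / 0.9. For a true 3-fold effect it is 3.00 / 3.05 / 3.68.

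**Adding the jackknife.** A simplified simulation of both steps (leave-one-out error, paired t test, one-sided 0.05 assumed because the plan gives no level) retains the true 1.4-fold effect in 15% of trials at a CV of 30% and 2% at a CV of 60%. The retained log effect averages 1.39 and 2.18 times the truth, and unadjusted 95% intervals among retained effects cover it in 85% and 51%. At a CV of 30% the likelihood ratio step alone gives 1.23 times, so the jackknife adds selection and does not shrink the estimate.

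**The case against.** The strongest reply is that the procedure is predictive by design. The plan says that the jackknife measures usefulness in a future individual and guards against trivial effects that NONMEM can detect. That purpose is legitimate and should stay. Every likelihood ratio test also requires fitting the covariate, so estimates will exist, and the Data Sharing Plan commits to releasing individual doses, times, concentrations, age, weight and sex with the software, so others could recompute dropped effects. This narrows the gap to one of planned reporting. It does not close it, because the aim stated in the outcome section is still not matched by a stated analysis.

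Four stronger readings are tempting, and the documents do not support them.

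- *Dropped covariates will be reported as having no effect.* The plan never says so; it is silent on how they are reported.
- *Retained effects are generally badly exaggerated.* This needs an effect that is small relative to its standard error. It does not arise at SD 0.2, or for a true 2-fold effect at SD 0.3.
- *For clearance, the design can certainly exclude 40%.* Back-calculating a Cl1 SD as range x sqrt(N) / 3.92 gives 17% from the uncorrected N = 11 range (20%), 8% from the N = 20 range (7%), and 42% from the corrected N = 11 range (50%). At 42% the 12 v 12 interval factor is 1.40, so the answer depends on which row is used.
- *40% is an equivalence margin.* It is a detectability figure derived from intravenous parameters, described as an effect that may matter.

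The crossover does not answer the point. It separates F from clearance within a subject, but between-subject variation in F remains the noise in a sex, age or weight contrast.

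**Conclusion.** The point holds as a cheap improvement. As written, the covariate analysis does not deliver what the outcome section promises: no estimate with an interval is planned for covariates that are dropped, and selection is ignored in those kept.

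The consequence is conditional. If the between-subject SD of log F is about 0.3 or more, a true 1.4-fold sex effect passes the likelihood ratio step in at most 57% of trials and is overstated on average when it does. From about 0.42, a dropped covariate's interval cannot exclude an effect of that size. At 0.2 there is little to correct. The plan's expectation of high variability in absorption suggests the upper part of the range, but it is qualitative and does not separate rate from extent.

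These figures rest on the assumed SDs, one contrast (sex, 12 v 12), a normal approximation and a simplified stand-in for the NONMEM fit. Age and weight contrasts were not calculated.

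**What to change.** Keep the stepwise and jackknife procedure for building the predictive model. Add to the Analytical Plan:

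1. One pre-specified full covariate model will be fitted, with sex, age and weight entered together on clearance and on intranasal bioavailability. Each estimate will be reported with its 95% interval whether or not the covariate is retained by the stepwise procedure.
2. Contrasts are fixed in advance: male v female; age over a stated difference, for example between the midpoints of the youngest and oldest strata (28.5 and 67.5 years, a difference of 39 years); weight over a stated difference. The plan gives "The sample size is increased to 24 to provide stratification by age (3 strata), weight (2 strata), and sex" as the reason for 24 subjects, but does not define the two weight strata, so that difference must be named.
3. Each interval will be read against the 40% effect that the plan calls possibly consequential, taken as 1/1.4 to 1.4. A covariate will not be described as having no consequential effect when its interval includes an effect of that size; it will be reported as undetermined.
4. Race and ethnicity will be reported descriptively if numbers are too small to model.

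The cost is a few extra model runs and one table, with no added subjects, samples or visits. Some covariates will be reported as undetermined. Intervals may widen where sex and weight are correlated: at SD 0.6 and an assumed correlation of 0.5, the factor goes from 1.62 to exp(1.96 x 0.245 / sqrt(1 - 0.25)) = 1.74. In the simplified simulation, intervals reported without selection covered the truth about 95% of the time and the estimates were not inflated.

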Prior to 2016, and to a considerable extent since, OXT was and is measured with antibody-based methods (EIA, ELISA, or RIA). Reported concentrations vary widely from study to study and, since development of accurate LC/MS assays, there is now considerable skepticism regarding the validity of the previous research and concerns that the older methods measure OXT degradation fragments (see [6] for review). Note in **Figure 1** the high baseline and wide variability in OXT concentrations and markedly different change in OXT concentrations after intranasal (i.n.) administration when ELISA and RIA methods are used compared to that of LC/MS, which unambiguously measures OXT [4; 5; 8; 9].

In preliminary data we infused OXT, 17  $\mu$ g, iv in 11 healthy men and women aged 22-58 years, measured plasma OXT with both LC/MS and with ELISA using validated protocols, and modeled the resultant data using NONMEM. Transient headache and facial flushing occurred when this dose was injected over 1 min in the first 3 individuals and these effects were reduced or eliminated with infusion over 10 min in the remainder of the subjects. PK analysis showed no effect of sex and a minor effect of body weight. Modeled data from the LC/MS analysis differ significantly from those using RIA assays after iv OXT injection [2; 7], which themselves differ widely (**Figure 2A**). In our study, ELISA assays showed more inter-individual variability (NONMEM estimates of variance due to assay for ELISA was 28% compared to 16% for LC/MS) and considerably different PK parameters than those obtained from LC/MS assays. Simulated target controlled infusions (TCI) based on

**Figure 1.** Mean plasma OXT via i.n. administration by various assays.

these models demonstrate the greater variability with ELISA than LC/MS (**Figure 2B**). At the same total dose of 17  $\mu$ g OXT, a 30 min TCI infusion using PK parameters using LC/MS assays would result in a targeted concentration nearly double that using PK from ELISA assays (80 vs 46 pg/ml for LC/MS vs ELISA).

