## Objectives

**Main objective** Model OXT concentrations in plasma after intravenous and i.n. administration in order to determine absorption rate and bioavailability of OXT in plasma after i.n. administration.

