## **STUDY DESIGN**

This is a sequential study of subjects, all of whom will receive, on different occasions, an intravenous infusion or intranasal (i.n.) sprays of oxytocin. Blood samples will be obtained thereafter in order to create a mathematical model to describe the concentrations of oxytocin in the blood over time (pharmacokinetics). In this study, healthy volunteers are recruited for two study drug visits. They will come to the CRU and have two IV catheters inserted, one in each arm for the first study visit. They will receive a 30 minute infusion through one of the IV catheters of oxytocin, 14  $\mu$ g, and blood will be obtained at several times over the next 120 minutes and the amount of oxytocin measured in the blood samples. They will come a second time to the CRU and have one IV inserted in their arm and self-administer i.n. oxytocin, 102 ug over 5 min and blood will be obtained several times over the next 60 minutes and the amount of oxytocin measured in the blood samples. Plasma oxytocin concentrations and individual subject characteristics (age, sex, weight, height, race, and ethnicity) will be analyzed by another group at Stanford University funded under the same NIH grant supporting the work at Wake Forest. The effect of these subject characteristics on the pharmacokinetics of oxytocin will be examined, since these characteristics alter concentration over time of some drugs. Should these characteristics alter oxytocin concentrations, we and others could adjust the dose of oxytocin to the individual.

The main purpose of this study is to sample blood and calculate the pharmacokinetics of oxytocin. We will also assess adverse events during the study.

The research participants will not benefit from this study, but the knowledge we get will be important not only to adjust oxytocin dose to individuals, but to study its possible effects on pain in a more precise way by controlling the amount of oxytocin in the blood circulation. The sample size we chose is needed to get an accurate estimate for the parameters in the pharmacokinetic model for the population in general, not just the subjects in this study.

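### The <20% precision and 40% covariate figures cover only the IV disposition parameters; no precision is calculated for intranasal bioavailability (F) or absorption rate, the main objective

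*Combined protocol and SAP*

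**What the plan says.** The main objective (Objectives) is to model plasma oxytocin after both routes "in order to determine absorption rate and bioavailability of OXT in plasma after i.n. administration". Outcome Measure(s) includes bioavailability and covariate effects in the description of the primary outcome.

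The precision argument is under Sample Size: "Table 1 shows the results of 1000 bootstrap replications of the original 11 individuals in the pharmacokinetic study". Those 11 people were dosed intravenously ("In preliminary data we infused OXT", Background). Table 1, captioned "Bootstrap parameter estimates of PK model", has rows for Cl1, V1, Cl2 and V2 at N=11 and N=20, and none for F or an absorption rate constant. The section concludes that 20 subjects give corrected 95% ranges within 20%, and that covariate effects of about 40% can therefore be distinguished. It raises N to 24 to allow stratification by age, weight and sex.

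The Analytical Plan repeats this as a statement that 20 individuals "will determine the PK parameters with a corrected confidence range < 20"%, repeats the 40% figure, and ends: "The crossover design permits accurate determination of i.n. bioavailability and dose linearity despite expected high inter-subject variability in absorption". Study Design puts it more broadly: "The sample size we chose is needed to get an accurate estimate for the parameters in the pharmacokinetic model for the population in general".

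No CV, CI width, simulation of precision or accuracy target is given for F or absorption rate. The 1% bioavailability in the Figure 3 legend serves to place sampling times.

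**The concern.** Intravenous data carry no information on F or on nasal absorption, so Table 1 cannot speak to the main objective. Because the Analytical Plan does not restrict its wording, a reader may apply both <20% and 40% to bioavailability.

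The crossover sentence is the only argument offered for F, and it is incomplete. Pairing IV with intranasal dosing deals with variation in clearance. The variation the sentence names is in absorption, and that stays in the standard error of the population F. If it is high, the estimate of F could be much less precise than the sample-size section leads one to expect, and later dosing work would rest on it.

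The sentence also promises dose linearity, which needs more than one intranasal dose level.

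**Working it through.** **1. Reproduce the plan's figure.** Table 1's range is (upper − lower)/mean. The correction is k divided by a chi-square quantile, "where k is N-1, the number of degrees of freedom". The printed factors come from the lower 5% quantile:

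- N=11: 10/3.940 = 2.54 (printed 2.54).
- N=20: 19/10.117 = 1.88 (printed 1.88).

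Corrected ranges at N=20 from the printed bounds:

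- Cl1: (1.01 − 0.95)/0.97 × 1.878 = 11.6% (printed 12%).
- V1: (10.6 − 9.6)/10.1 × 1.878 = 18.6% (printed 18%).
- V2: (7.3 − 6.7)/7.0 × 1.878 = 16.1% (printed 16%).
- Cl2: bounds too rounded to use; the printed 8% range gives 8 × 1.878 = 15.0% (printed 16%).

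So <20% follows from the table, for these four parameters. The bootstrap itself cannot be rerun from the documents, and this point takes Table 1 as printed. One caution: the N=20 ranges are 0.28 to 0.35 of the N=11 ranges, whereas root-n scaling gives √(11/20) = 0.74, so the sponsor should check that bootstrap separately.

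**2. What pairing removes.** With clearance CL_i unchanged between visits, AUC_IV = D_IV/CL_i and AUC_IN = F_i × D_IN/CL_i. The dose-adjusted ratio is F_i, and CL_i cancels. Each subject supplies one F_i, so the standard error of mean ln F is at least σ/√N, where σ² = ln(1 + CV²) and CV is the between-subject CV of F. No pairing reduces σ.

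**3. Size, by assumption.** The plan says only that variability in absorption is high, so the CV is assumed over 30% to 100%. With log-normal F and N=24, h = t(0.975, 23) × σ/√24 with t = 2.069, and the full width relative to the geometric mean is exp(h) − exp(−h). The plan's correction at N=24 is 23/13.091 = 1.757.

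| Assumed CV of F | σ | h | 95% CI width | With the plan's correction |
|---|---|---|---|---|
| 30% | 0.294 | 0.124 | 25% | 44% |
| 50% | 0.472 | 0.199 | 40% | 71% |
| 75% | 0.668 | 0.282 | 57% | 100% |
| 100% | 0.833 | 0.352 | 72% | 126% |

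Solving for a width of 20% gives a CV of about 24%, or about 13.5% with the correction. Within-subject estimation error is ignored, so the uncorrected widths are lower bounds for each CV.

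**4. Covariates on F, illustrative.** Assume two groups of 12, a t-test on ln F with 22 df, and two-sided alpha 0.01 (the plan's significance level).

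| Assumed CV of F | Power, 40% increase (ratio 1.4) | Power, 40% decrease (ratio 0.6) | Ratio detectable with 80% power |
|---|---|---|---|
| 30% | 51% | 91% | 1.6 |
| 50% | 17% | 45% | 2.0 |
| 75% | 8% | 20% | 2.7 |
| 100% | 5% | 12% | 3.5 |

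**5. Dose linearity.** Background describes two intranasal doses on different occasions. Methods and Measures, Study Design, Study Visit 2 and Outcome Measure(s) describe one intranasal dose level, 102 µg. One level cannot show linearity. No assumed CV is needed to see this.

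**The case against.** A reader might infer that the crossover claim is false, or that the trial is too small for its main objective. The documents do not support that. They set no threshold for accurate and give no CV for F, so widths from an assumed CV cannot refute the sentence. A width of 25% to 40% may be adequate for a quantity whose only stated prior value is an assumed 1%.

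The crossover rationale is also partly right. Take an assumed clearance CV of 20% to 30% and a parallel design with 12 IV and 12 intranasal subjects, where h = t(0.975, 22) × √[(σ_F² + σ_CL²)/12 + σ_CL²/12]. The widths would be 49% to 62% at a CV of F of 30%, and 67% to 77% at 50%. The crossover gives 25% and 40%. The rationale needs qualifying, not deleting.

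The <20% statement in the Analytical Plan is introduced as a bootstrap result, so a careful reader could trace it back to Table 1 and limit it accordingly. That it covers F is an inference from loose wording.

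The power figures depend on choices the plan does not make. The 40% effect has no stated direction, and at a CV of 30% direction alone moves power from 51% to 91%. The plan uses a one-df likelihood ratio test; a normal approximation gives 59% rather than 51% for the 1.4-fold effect at that CV. Age and weight may enter as continuous covariates.

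These objections limit the verdict and make the covariate figures illustrative only. They do not supply a precision for F or absorption rate.

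**Conclusion.** The point holds in this form: the <20% range and the 40% covariate figure are derived for Cl1, V1, Cl2 and V2 from IV-only data, are stated more widely than that, and leave the main objective without any calculated precision. The claim of accurate bioavailability is unsupported. If the plan's 20% criterion were meant for F, it would be met at N=24 only with a CV of F of at most about 24%, or 13.5% with the plan's correction; variability described as high would probably exceed that. This rests on log-normal F, stable clearance between visits, negligible within-subject error and an assumed CV. The absence of a calculation for F, and the conflict over the number of intranasal dose levels, rest on no assumption. The fault lies in what the plan says about its precision; the documents give no ground for calling the sample size inadequate.

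**What to change.** 1. In Sample Size and the Analytical Plan, state that the <20% range and the 40% covariate figure apply to the IV disposition parameters only.
2. Add the expected CI width for F and for absorption rate at N=24 over a stated range of CVs, preferably by simulating the combined IV and intranasal design with its sampling times. Give detectable covariate ratios for both increases and decreases, labelled illustrative.
3. Reword the crossover sentence: pairing separates each subject's F from that subject's clearance, but leaves between-subject variability in F in the population estimate.
4. Reconcile Background and the dose-linearity claim in the Analytical Plan with Methods and Measures, Study Design, Study Visit 2 and Outcome Measure(s) on the number of intranasal dose levels.

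The cost is some rewording, a short table and one simulation. Enrolment does not change. The downside is that the stated precision for F will look less favourable.
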